5.2.2 Change from Baseline in Body Mass Index (BMI)

Change from Baseline in BMI at 13 weeks will be compared between groups. Height is collected at Visit 1; weight is collected at Visit 1 and at Visit 8. Change in BMI is calculated as follows:

Change from Baseline in
$$BMI = BMI$$
 (Visit 8) – BMI (Visit 1)

where BMI at baseline (Visit 1) is calculated as:

 $BMI (Visit 1) = \frac{Weight at Visit 1 (kg)}{(Height at Visit 1 (m))^2}$

and BMI at follow-up (Visit 8) is calculated as:

$$BMI (Visit 8) = \frac{Weight at Visit 8 (kg)}{(Height at Visit 1 (m))^2}$$

If a participant's weight is reported in pounds, the following conversion will be performed:

$$Weight (kg) = \frac{Weight (lbs)}{2.2}$$

If a participant's height is reported in inches, the following conversion will be performed:

$$Height(m) = \frac{Height(in) * 2.54}{100}$$

5.2.3 Change from Baseline in Total Daily Insulin (TDI)

Change from Baseline in TDI (units/kg) at the end of the 13-week randomized period will be compared between groups. The insulin requirements will be collected at Visit 3 and at Visit 8, and change in TDI will be calculated as follows:

TDI (change from Baseline,
$$\frac{units}{kg}$$
) = $\frac{TDI (13 weeks) - TDI (Visit 3)}{subject's weight at Visit 1}$

5.2.4 Additional CGM-Derived Endpoints

The following additional CGM-derived endpoints, such as coefficient of variation (CV), percentage of time >250 mg/dL, percentage of time <54 mg/dL (superiority), TIR during daytime and nighttime hours will be compared between groups at the end of the 13-week randomized period.

CV is calculated per participant as follows, then summarized and compared between groups:

$$CV(\%) = \frac{SD \ of \ glucose}{mean \ glucose}$$

5.2.5 Episodes of Severe Hypoglycemia and DKA

As the number of episodes (events) of severe hypoglycemia (SH) and DKA are of significant interest, statistical testing will be performed for the rate of SH (and DKA) if there are ≥5 events (of SH or DKA, respectively) combined across both treatment groups during the randomized period. The rates will be calculated as the number of events per 100 person years. The rates will be compared using a Poisson regression with site as a random effect. The amount of follow-up will be included as an offset term. If a participant withdraws from the study prior to Visit 8 then the later of the last visit date, last AE date or

final status date (if known) will be used as the last day of the randomized period for the purpose of calculating follow-up time for safety endpoints.

If there are concerns with model convergence (e.g., due to zero events in one group), Fisher's exact test for the number of events will be used instead.

The number of severe hypoglycemia and DKA adverse events, and the number and percent of participants with at least one event in each group will be summarized.

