12.5 General Statistical Methods

Standard statistical methods will be employed to analyze all data. Data collected in this study will be presented using summary tables and participant data listings. Unless otherwise noted, all p-values will be considered significant at a two-sided significance level of 5%. Continuous variables will be summarized using descriptive statistics, including count, mean, median, standard deviation (SD), minimum and maximum. Where appropriate, 95% two-sided confidence intervals for the means or medians will be presented. If the observed data are found not to follow a normal distribution, appropriate non-parametric methods may be employed. Categorical variables will be summarized by frequencies and percentages. Unless explicitly stated otherwise, percentages will utilize a denominator corresponding to the number of unique participants.

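### The severe hypoglycemia and DKA tests in SAP 5.2.5 count events and make no allowance for repeats in one participant, so their type I error can exceed 5% if events cluster

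*SAP*

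**What the plan says.** SAP 5.2.5 tests SH and DKA separately, each only "if there are ≥5 events (of SH or DKA, respectively) combined across both treatment groups". The numerator is events: "The rates will be calculated as the number of events per 100 person years". The method is stated as "The rates will be compared using a Poisson regression with site as a random effect", and "The amount of follow-up will be included as an offset term". No participant-level random effect, dispersion parameter or robust variance is named.

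If the model may not converge (the example given is an arm without events), Fisher's "exact test for the number of events will be used instead". No denominator is stated for that table. The same section says that "the number and percent of participants with at least one event in each group will be summarized", but those participant counts are not tested.

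Nothing elsewhere supplies a correction:

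- Protocol 12.3.3 repeats the five-event trigger and names no method.
- The rule that counts a repeated event once per participant (Protocol 12.3.1, SAP 6.5) governs the adverse-event tables, not this test.
- SAP 5.2.6 treats exploratory results as not supporting clinical claims and makes no multiplicity adjustment.

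**The concern.** Fisher's exact test compares independent yes/no units. An event count is not a count of such units once a participant contributes two or more events: the table then treats one person's repeats as if they came from different people. Follow-up time also drops out, although that matters little here.

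The Poisson model has the same weakness in milder form. Given site, it takes the variance of a participant's count to equal its mean. A site effect describes differences between sites and does not absorb repeats within a person.

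SH and DKA are the events that readers of a trial of automated insulin delivery will look for. A few participants with repeats could produce a nominally significant difference between arms, in either direction, where none exists.

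**Working it through.** **Inputs.** From the documents: 170 randomized at 2:1 (SAP 4.1), so about 113 Intervention and 57 Control; 13 weeks of follow-up; at least 5 events before testing; two-sided 5% (Protocol 12.5). The plan gives no event rate, repeat rate or error rate for SH or DKA, so there is no figure of its own to reproduce. Everything about rates and clustering below is an assumption.

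**Step 1: the fallback.** I took participants per arm as the missing denominator. If all *k* units fall in Control, the two-sided Fisher p-value for k = 1, 2 or 5 is C(57,k)/C(170,k):

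- k = 1: 57/170 = 0.335
- k = 2: (57×56)/(170×169) = 0.111
- k = 5: (57×56×55×54×53)/(170×169×168×167×166) = 0.0038

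Five Control events against none are entered as k = 5 whoever had them. By participant, the same data give 0.335, 0.111 or 0.0038 for one, two or five people.

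Other cases, as event-count p against participant p:

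- 1 vs 6 events from 1 vs 2 participants: 0.0061 against 0.26.
- 10 vs 0 events from five Intervention participants with two each: 0.032 against 0.17.
- 5 vs 0 events in Intervention is not significant even on events (p = 0.17), because that arm is larger.

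A conditional binomial test on person-time gives 0.0042 for 0 vs 5, so losing the offset is not the problem. The repeats are.

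**Step 2: the Poisson model.** Suppose a fraction π of participants has K ≥ 1 events and the rest have none. The variance-to-mean ratio of the count is E[K²]/E[K] − π·E[K]; Poisson assumes 1. Take π = 3% and K = 1 + Poisson(1):

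- E[K] = 2 and E[K²] = 1 + 2² = 5.
- Ratio = 5/2 − 0.03×2 = 2.44, so the standard error is too small by a factor √2.44 = 1.56.
- With no repeats the ratio is 1 − 0.03 = 0.97, and there is no inflation.

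**Step 3: the whole procedure under the null.** I simulated equal arms, 3% of participants affected, testing only with at least 5 events, a Wald test of the Poisson rate ratio, and Fisher on events if an arm had none (100,000 trials per row; no site heterogeneity or dropout). The implied rate is 0.03 × E[K] / (13/52.18 years); for E[K] = 2 that is 24 per 100 person-years.

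| Further events per affected participant | Rate per 100 person-years | SAP rule rejects (of tested trials) | Fallback used (of tested) | Fallback rejects: events | Fallback rejects: participants |
|---|---|---|---|---|---|
| None | 12 | 1.3% | 8% | 5% | 5% |
| Mean 0.2 | 14 | 4.3% | 10% | 15% | 6% |
| Mean 1, at most two events each, both arms | 20 | 9.0% | 13% | 32% | 7% |
| Mean 1, no cap | 24 | 16.8% | 15% | 49% | 6% |

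Fisher's test on participants, used in all tested trials, rejects about 3% in every row.

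**Step 4: a different clustering model.** With gamma frailty between participants (variance 0 to 20) and no cap on repeats, the SAP rule rejects 0.9% to 5.1% of tested trials at 10 events per 100 person-years, 2.4% to 10.6% at 20, and 3.3% to 19.8% at 40.

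**The case against.** Four points on the other side carry weight.

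- **Status.** SH and DKA episodes are exploratory, and SAP 5.2.6 disclaims clinical claims from them. Protocol 11.8 even says that exploratory endpoints will not be formally tested, which does not sit with the test planned in Protocol 12.3.3 and SAP 5.2.5. This lowers the weight but does not make the p-value valid.
- **Few events.** Recent SH and most recent DKA are exclusions (Protocol 7.1.2.2). At about 10 events per 100 person-years, Step 4 shows a type I error of at most about 5% even with strong clustering. This stands.
- **Repeats are limited.** Protocol 10.1 ends investigational-device use after two SH events, two DKA episodes or one of each. Repeats there would ordinarily stop at about two. No equivalent is stated for Control participants' own pumps, and pairs of events still inflate the error (third row of the table).
- **Repeats are visible.** Participants with an event are reported beside the event count. That helps a careful reader, who would then see a sound table next to an unsound p-value.

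A reader might go further and infer that the error rate is about one half. The documents do not support this: that figure applies only within the zero-cell fallback, about 15% of tested trials in the most clustered row, under rates the plan never states. A likelihood-ratio Poisson test would look worse (about 29%), but the SAP does not name one, and it already rejects about 10% without repeats.

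Nor can one infer that the flaw favours the device. In the uncapped row, about 85% of false rejections in the fallback showed an excess on Intervention, since the smaller Control arm is more often empty. Over the whole procedure the share was about 41%.

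**Conclusion.** The point holds as a defect of specification. As written, both tests treat repeat events in one participant as independent, and the fallback cannot tell five affected participants from one. The fallback p-value is invalid whenever anyone contributes more than one event; this follows from the text and needs no assumption about rates.

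The practical size does depend on assumptions. The whole procedure rejects about 1% of tested null trials with no repeats, about 4% with few, and about 9% to 17% at roughly 20 to 24 events per 100 person-years with about 1.6 to 2 events per affected participant. Within the zero-cell fallback alone, the last range becomes about 32% to 50%, against 6% to 7% by participants. The supportable statement is that the error can exceed 5% if events cluster, not that it will. Given the exploratory status and the limit on repeats in one arm, this is a modest but worthwhile correction.

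**What to change.** Amend SAP 5.2.5 in two places.

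1. Run the Fisher fallback on participants with at least one event, out of participants randomized in each arm.
2. Compare rates with a permutation test of events per person-year, permuting arm labels within site and keeping each participant's events and follow-up together. This handles both repeats and zero cells, so the fallback would seldom be needed.

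Negative binomial regression or a participant-clustered robust variance would be weaker choices. With about five events the dispersion is barely estimable, and the rate ratio breaks down when an arm has no events. In the gamma-frailty simulations the robust variance reached 7.2% in the harshest case.

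The SAP should also reconcile this test with the statement in Protocol 11.8 on exploratory endpoints, for instance by calling the p-value nominal.

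The cost is a few sentences and no new data, visits or participants. The downside is fewer nominally significant results when events cluster, and a fallback that no longer uses information on repeats.

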5.2.6 Analysis Methods for Exploratory Endpoints

The mITT analysis set will be the main analysis set used to analyze these endpoints.

For continuous endpoints, mean and standard deviation or median and interquartile range, as appropriate, in each group will be presented. Continuous endpoints will be analyzed using a repeated measures linear mixed effects with the endpoint at baseline and at 13 weeks as the dependent variable. The correlation between baseline and follow-up will be modelled using an unstructured covariance matrix. The model will include randomized treatment group, age, sex, and duration of diagnosis as fixed effects and site as a random effect. This model adjusts for baseline value of the endpoint by forcing the treatment groups to have the same mean value at baseline. If values are highly skewed, then robust regression using M-estimation will be used instead, as described above for the secondary endpoints.

For binary endpoints, number and percent of participants in each group will be presented. Binary endpoints will be analyzed using a logistic mixed effects model with the endpoints as the outcome. The following variables will also be included in the model as fixed effects: randomized treatment group, age, sex, duration of diagnosis, and baseline continuous value of the outcome being tested. In addition, the model will adjust for site as a random effect. A 95% confidence interval for the treatment group adjusted risk difference will be produced using parametric bootstrapping. Analysis of binary endpoint will be based on complete cases only.

Since the results of exploratory endpoint analyses will not be used to support clinical claims, no adjustment for multiplicity will be performed.

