4 ANALYSIS OF PRIMARY ENDPOINT

4.1 SAMPLE SIZE

The sample size estimation is based on the following assumptions:

- Power of 90% and two-sided significance level of 5%
- Difference between groups of 10% in TIR 70-180 mg/dL
- Standard deviation of 16.5% in each group
- 2:1 randomization (Intervention:Control)

Under these assumptions, a total sample size of 131 participants is required (87 Intervention, 44 Control). To allow for pre-randomization attrition of up to 15%, and post-randomization attrition of up to 22.9%, a total sample size of up to 200 will be enrolled to give 170 participants randomized and 131 participants completing the 13 weeks. The anticipated difference in TIR 70-180 mg/dL was projected from the OP5 pivotal study.

The sample size calculations were performed using PASS 2021.

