Binary PRO-derived endpoints will be presented as number and percent of participants achieving treatment success with corresponding 95% asymptotic confidence limits in each group. Binary endpoints will be analyzed using a logistic mixed effects model with the endpoints as the outcome. The following variables will also be included in the model as fixed effects: randomized treatment group, age, sex, duration of diagnosis, and baseline continuous value of the outcome being tested. In addition, the model will adjust for site as a random effect. A 95% confidence interval for the treatment group adjusted risk difference will be produced using parametric bootstrapping.

Standard residual diagnostics will be performed for all secondary analyses. Residual values will be examined to confirm an approximate normal distribution. If values are highly skewed, then robust regression using M-estimation will be used instead. In this case, the model will include the endpoint at 13 weeks as the dependent variable, baseline value of the endpoint as a covariate, and missing data will be handled using multiple imputation.

The secondary analyses will utilize the mITT analysis set, and will be tested at a two-sided significance level of 5% or a one-sided significance level of 2.5%, as appropriate. If there is evidence of heterogeneity either across countries or study sites based on the poolability analysis, a random effect for country or site, as appropriate, will also be included.

The secondary endpoints will be testing in the following order:

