5.2.1 A1C at 13 Weeks and Improvement from Baseline in A1C

Corelab A1C will be collected at Visit 1 and Visit 8. A1C will be evaluated based on the following exploratory endpoints:

- Proportion of participants with A1C <7% at 13 weeks
- Proportion of participants with A1C <8% at 13 weeks
- Proportion of participants with ≥1% improvement from baseline (Visit 1) in A1C at 13 weeks, where improvement is calculated as follows:

Improvement in A1C = A1C (Visit 1) – A1C (13 weeks)

• Proportion of participants with ≥10 relative percentage point improvement from baseline (Visit 1) in A1C at 13 weeks, where relative percentage point improvement is calculated as follows:

 $Relative improvement in A1C = \frac{A1C (Visit 1) - A1C (13 weeks)}{A1C (Visit 1)} * 100\%$

Proportion of participants with either ≥1% improvement from baseline (Visit 1) in A1C at 13 weeks, or ≥10 relative percentage point improvement from baseline (Visit 1) in A1C at 13 weeks

The endpoints will be compared between groups. The denominator for the calculation of these endpoints includes all participants for whom an A1C at 13 weeks is available. Further, for the endpoints involving improvement in A1C, the A1C at baseline (Visit 1) will also need to be available.

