7.6.1.1 Missing Data Handling for A1C- and PRO-Derived Endpoints

It is likely that at least some participants do not contribute data for A1c, BMI, or Patient-Reported Outcomes (PROs) (e.g., due to early withdrawal). For the main analysis of such endpoints, missing values for the participants in the mITT analysis set will be imputed as follows:

- If a participant withdrew from the study early and provided an endpoint value collected within 13-week analysis window (Section 7.1), the last known value will be used in the analysis of the endpoint.
- If a participant is confirmed to have withdrawn early from the study due to unsatisfactory treatment or potential loss of efficacy outside of the analysis window (Section 7.1), the change from baseline in a specific endpoint will be assumed to be zero (e.g., no change).
- If a participant does not provide a value for the specific endpoint for other reason (e.g., lost sample, participant lost to follow-up), the endpoint data will be imputed.

This allows for all participants in the mITT analysis set to be included in the analysis of these endpoints.

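### Responder endpoints: the SAP has two incompatible missing-data rules for the A1C proportions, an unfinished rule for the tested PRO proportions, and a zero-change rule that can score a treatment-failure withdrawal as a success on HCS ≥3 or A1C <8%

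*SAP*

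**What the plan says.** **A1C proportions (five, exploratory).** SAP 5.2.1: "The denominator for the calculation of these endpoints includes all participants for whom an A1C at 13 weeks is available". The improvement endpoints also need a baseline value. SAP 5.2.6 gives the model and adds: "Analysis of binary endpoint will be based on complete cases only". The same section names mITT as the main analysis set.

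**PRO proportions (three, secondary and tested).** T1-DDS, DQOL-brief and HCS ≥3 are SAP 5.1.9 to 5.1.11, the last three steps of the fixed sequence. SAP 5.1 says of them: "Binary endpoints will be analyzed using a logistic mixed effects model with the endpoints as the outcome". It contains no complete-case sentence for these endpoints.

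**The filling-in rule.** SAP 7.6.1.1 is headed "Missing Data Handling for A1C- and PRO-Derived Endpoints" and sets the main analysis:
- For an early withdrawal with a value inside the 13-week window, "the last known value will be used in the analysis of the endpoint".
- For a confirmed withdrawal outside the window because of unsatisfactory treatment or possible loss of efficacy, "the change from baseline in a specific endpoint will be assumed to be zero (e.g., no change").
- For any other reason, the value is imputed. No method is named.

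It concludes: "This allows for all participants in the mITT analysis set to be included in the analysis of these endpoints".

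**Attrition.** SAP 4.1 allows "post-randomization attrition of up to 22.9" percent, from 170 randomized to 131 completing.

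**Precedence.** The SAP prevails over the protocol (SAP 1, Protocol 12.7). Nothing ranks one SAP section over another.

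**The concern.** A participant who leaves early without an in-window A1C is absent from the A1C proportions under 5.2.1 and 5.2.6, but present under 7.6.1.1. Whoever writes the analysis program must choose, possibly after seeing the data.

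For the PRO proportions the question is how 7.6.1.1 is to be carried out. The direct-likelihood sentence in SAP 5.1 serves the continuous model, which has baseline and 13 weeks as outcomes. The logistic model has one outcome, and a missing outcome drops out unless it is filled first. The SAP does not say whether the score or the responder status is imputed, or by what method. The multiple imputation in SAP 4.3.2 is written for TIR.

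The third issue is one of scoring. Zero change means that the 13-week value equals baseline. On an endpoint defined by a level, this keeps a baseline success as a success, even though the reason for leaving was that treatment did not work.

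**Working it through.** **1. The plan's own figures.** Inputs from SAP 4.1: difference 10, SD 16.5, two-sided 5%, power 90%, ratio 2:1. For 87 and 44, the noncentrality is 10 / (16.5 × √(1/87 + 1/44)) = 3.28, and the two-sample t test has power 0.902. Then 131 / (1 − 0.229) ≈ 170 and 170 / 0.85 = 200. The figures reproduce. No power is given for any responder endpoint.

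**2. Participants in dispute.** 170 − 131 = 39. With 2:1 randomization (113 and 57), that is 113 − 87 = 26 Intervention and 57 − 44 = 13 Control. This is a ceiling. An early withdrawal with an A1C within 2 weeks of day 90, or a PRO within 5 weeks (SAP 7.1.2), is used under either rule.

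**3. Where zero change can produce a success.**

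| Endpoint | Status in SAP | Zero change gives |
|---|---|---|
| A1C ≥1% improvement; ≥10% relative; either | exploratory | always failure |
| T1-DDS improvement ≥0.19 | tested | always failure |
| DQOL-brief improvement ≥0.5 SD | tested | always failure |
| A1C <7% | exploratory | success only if central-lab baseline was below 7%; entry requires point-of-care 7.0–11.0% |
| A1C <8% | exploratory | success if baseline was below 8% |
| HCS ≥3 | tested, last in sequence | success if baseline was ≥3 |

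For A1C <8%, the recruitment rule (at least 80% at 8% or above) leaves up to 20% below 8%. If withdrawals have the same mix, 0.20 × 39 = 7.8, so about 8 people (5.2 Intervention, 2.6 Control), and only if all 39 were zero-change. The documents give no baseline HCS distribution. If 30% to 70% start at ≥3, the same ceiling is 0.30 × 39 ≈ 12 to 0.70 × 39 ≈ 27 people.

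**4. Effect on the estimated difference.** Assumptions, none from the documents: completer rates 55% and 35%; a share s of the lost are zero-change, with 20% of them baseline successes; the rest respond at completer rates. Rate in an arm = [completers × p + lost × (s × 0.20 + (1 − s) × p)] / randomized.

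| Losses 26/13 | Intervention | Control | Difference |
|---|---|---|---|
| Complete cases | 55.0% | 35.0% | 20.0 |
| s = 0.25 | (47.85 + 26 × 0.4625)/113 = 53.0% | (15.4 + 13 × 0.3125)/57 = 34.1% | 18.8 |
| s = 0.50 | (47.85 + 26 × 0.375)/113 = 51.0% | (15.4 + 13 × 0.275)/57 = 33.3% | 17.7 |

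The complete-case SE is √(0.55 × 0.45/87 + 0.35 × 0.65/44) = 9.0 points, so the shifts of 1.2 and 2.3 points are about 0.1 and 0.3 SE.

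**5. Effect of the false successes alone.** At s = 0.50, scoring all zero-change withdrawals as failures gives (47.85 + 26 × 0.275)/113 = 48.7% and (15.4 + 13 × 0.175)/57 = 31.0%, a difference of 17.7. Each arm's rate falls by about 2.3 points, and the difference hardly moves. If losses are 32/7 instead, the difference is 16.0 with baseline successes kept ((44.55 + 32 × 0.375)/113 = 50.0%; (17.5 + 7 × 0.275)/57 = 34.1%). It is 14.4 with them scored as failures ((44.55 + 32 × 0.275)/113 = 47.2%; (17.5 + 7 × 0.175)/57 = 32.9%). So the scoring rule shifts the comparison mainly when losses are unequal.

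**The case against.** The strongest reply is that little of consequence is affected. The contradiction touches only the A1C proportions, which SAP 5.2.6 says will not support clinical claims and Protocol 11.8 excludes from formal testing. The PRO proportions have one rule, not two. The false-success route is closed for every change-based endpoint. On HCS ≥3 it matters for the formal test only if the primary endpoint and all ten earlier secondary steps succeed. Early Withdrawal visits collect A1C and questionnaires, so fewer than 39 may lack a usable value. Zero change is also confined to confirmed withdrawals for lack of effect. All of this stands, and it limits the size of the point.

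Three stronger readings are tempting, and the documents do not support them:
- *The complete-case rule also drops PRO withdrawals.* Section 5.2.1 concerns A1C, and 5.2.6 is the exploratory methods section. SAP 7.7 refers to the methods for secondary and exploratory endpoints, which does not clearly carry the sentence over to the tested PRO proportions.
- *All 39 losses count as non-responders.* With the assumed rates this gives 15.3 points for losses of 26/13 and 8.7 for 32/7. Neither SAP rule prescribes it.
- *Complete cases favour the device whenever more people leave the Intervention arm.* Unequal loss alone does not bias a covariate-adjusted logistic model. Those who leave must also differ in outcome, given arm and covariates.

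What the reply does not answer is that two stated rules exclude each other, that a tested endpoint has no named imputation method, and that a literal rule gives a wrong score on that endpoint.

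**Conclusion.** The point holds in three limited parts.

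1. For the five exploratory A1C proportions, 5.2.1 and 5.2.6 contradict 7.6.1.1. Only participants without an in-window value are affected, at most 39 of 170 at planned attrition.
2. For the three tested PRO proportions there is an incomplete rule, not a conflict. The imputation method and the step from score to responder status are missing.
3. Zero change misclassifies some treatment-failure withdrawals on HCS ≥3 and, if 7.6.1.1 governs, on A1C <8%. A1C <7% is affected only marginally.

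Under the stated assumptions, the choice of rule moves a 20.0-point difference to about 18.8 or 17.7. These figures come from unadjusted proportions, and they rest on assumed response rates and an assumed zero-change share. The primary endpoint is untouched. The change is worth making before unblinding because it settles the scoring of a tested endpoint at little cost.

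**What to change.** Adopt one rule in the mITT set for all eight responder endpoints, and refer to it from SAP 5.1, 5.2.1, 5.2.6 and 7.6.1.1:

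- Use in-window values as now.
- For values missing for other reasons, multiply impute the continuous 13-week A1C or PRO score by the SAP 4.3.2 approach (100 data sets; treatment, baseline score, age, sex, duration of diagnosis). Derive responder status in each data set, fit the logistic mixed model and pool.
- Score confirmed withdrawals for unsatisfactory treatment or loss of efficacy outside the window as non-responders, whatever their baseline. This gives the same result as zero change on the change-based endpoints, and differs only where baseline already met an absolute cut-off.
- Keep complete cases as a sensitivity analysis, and amend the two sentences in 5.2.1 and 5.2.6 to say so.
- The DQOL-brief cut-off is half an SD of the change score. State that it is computed once, and from which participants, so that it does not vary between imputed data sets.

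The cost is SAP wording and a little programming. Reported responder differences may become slightly smaller.
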